## Appendix B. VT-1598 TOXICITY GRADING CRITERIA FOR NORMAL HUMAN SUBJECTS

Adverse Events*	Mild (Grade 1)	Moderate (Grade 2)	Severe (Grade 3)
Laboratory Adverse Events* (Blood, Serum or Plasma)			
Sodium (hyponatremia) – mEq/L	131-132	129-130	<129
Sodium (hypernatremia) – mEq/L	144-145	146-147	>147
Potassium (hyperkalemia) – mEq/L	5.2 – 5.4	5.5 – 5.6	>5.6
Potassium (hypokalemia) – mEq/L	3.2-3.4	3.0 – 3.1	<3.0
Phosphorus – mg/dL (Hypo)	2.3 – 2.4	2.1 – 2.2	≤2.0
Phosphorus – mg/dL (Hyper)	N/A	N/A	N/A
Magnesium – mg/dL	1.3-1.5	1.1-1.2	<1.1
Gamma- Glutamyl Transferase (GGT) – Male – U/L	N/A	N/A	N/A
Gamma- Glutamyl Transferase (GGT) – female – U/L	N/A	N/A	N/A
Glucose (hypoglycemia) – mg/dL	65 – 69	55 – 64	<55
Glucose (hyperglycemia) – mg/dL Fasting	106 – 125	126 – 200	>200
Blood Urea Nitrogen – mg/dL	21-26	27 – 31	> 31
Creatinine (Male) – mg/dL	1.3 – 2.0	2.1-2.3	>2.3
Creatinine (Female) – mg/dL	1.0 – 1.7	1.8 – 2.0	>2.0
Calcium (hypocalcemia) – mg/dL	8.0 – <LLN	7.5 – 7.9	<7.5

Adverse Events*	Mild (Grade 1)	Moderate (Grade 2)	Severe (Grade 3)
Calcium (hypercalcemia) – mg/dL	10.4-10.8	10.9-11.4	>11.4
Chloride – mEq/L	N/A	N/A	N/A
CPKt-U/L (Male)	1.1 - ≤ 1.5 x ULN	>1.5 - ≤ 3.0 x ULN	>3.0 ULN or higher
CPKt – U/L(Female)	1.1 - ≤ 1.5 x ULN	>1.5 - ≤ 3.0 x ULN	>3.0 ULN or higher
A.M. Cortisol (serum, drawn prior to 10 a.m.) – ug/dL	1-10% below LLN	10-25 % below LLN	>25% below LLN with or without symptoms
Albumin (hypoalbuminemia) – g/dL	2.8 – 3.4	2.5 – 2.7	< 2.5
AST – U/L	1.1 - ≤ 2.5 x ULN	>2.5 - ≤ 5.0 x ULN	>5.0 x ULN or higher
ALT – U/L	1.1 - ≤ 2.5 x ULN	>2.5 - ≤ 5.0 x ULN	>5.00 x ULN or higher
Total Bilirubin (serum) – mg/dL	1.1 - ≤ 1.25 x ULN	>1.25 - ≤ 1.50 x ULN	>1.50 x ULN or higher
Direct Bilirubin – mg/dL	1.1 - ≤ 1.25 x ULN	>1.25 - ≤ 1.50 x ULN	>1.50 x ULN or higher
Indirect Bilirubin – mg/dL	1.1 - ≤ 1.25 x ULN	>1.25 - ≤ 1.50 x ULN	>1.50 x ULN or higher
Amylase – U/L	1.1 - ≤ 1.5 x ULN	>1.5 - ≤ 2.0 x ULN	>2.0 x ULN or higher
Lipase – U/L	1.1 - ≤ 1.5 x ULN	>1.5 - ≤ 2.0 x ULN	>2.0 x ULN or higher
Hemoglobin (Male) – g/dL	11.2 - 12.2	10.0 – 11.1	<10.0
Hemoglobin (Female) – g/dL	9.8 - 10.8	8.5 - 9.7	<8.5
WBC Increase – cell/mm 	10,001– 15,000	15,001 – 20,000	> 20,000
WBC Increase – cell/mm  (African America Males)	9,001 – 14, 000	14,001 – 19, 000	>19,000
WBC Increase – cell/mm  (African American Females)	11,001 – 15,000	15,001 – 20,000	>20,000

Adverse Events*	Mild (Grade 1)	Moderate (Grade 2)	Severe (Grade 3)
WBC Decrease – cell/mm 	2,500– 3,999	1,500 – 2,499	< 1,500
WBC Decrease – cell/mm  (African American Males)	2,200 – 2,499	1,200 – 2,199	<1,200
WBC Decrease – cell/mm  (African American Females)	2,200 – 2,499	1,500 – 2,199	<1,500
Neutrophils Decrease – cell/mm 	1,300 – <1,699	1,000 – 1,299	< 1,000
Neutrophils Decrease – cell/mm  (African American Males)	1,000 – 1,299	800 - 999	<800
Neutrophils Decrease – cell/mm  (African American Females)	1,100 – 1,299	1,000 – 1,099	<1,000
Platelets Decreased - cell/mm 	120,000 – <150,000	100,000 – 119,999	<100,000
PT (prothrombin time) – seconds	11.6 – 12.6	12.7 – 13.7	>13.7
PT INR (Prothrombin INR)	1.2-1.4	1.5-1.9	2.0 or higher
PTT (partial thromboplastin time) –seconds	30.1 – 36.8	36.9 – 43.6	>43.6
Total Protein – g/dL	5.5 - 5.9	5.0 - 5.4	<5.0
Alkaline phosphatase – IU/L (Male)	1.1 - ≤ 2.0 x ULN	>2.0 - ≤ 3.0 x ULN	>3.0 x ULN or higher
Alkaline phosphatase – IU/L (Female)	1.1 - ≤ 2.0 x ULN	>2.0 - ≤ 3.0 x ULN	>3.0 x ULN or higher
Hematocrit (Male) - %	33.0 -36.1	29.8 - 32.9	< 29.8
Hematocrit (Female) - %	29.5 - 32.6	26.0 – 29.4	< 26.0
RBC (Male) – x 10  /uL	3.9 - 4.1	3.4 - 3.8	< 3.4

Adverse Events*	Mild (Grade 1)	Moderate (Grade 2)	Severe (Grade 3)
RBC (Female) – x 10  /uL	3.5 - 3.7	3.0 - 3.4	< 3.0
Lymphocytes - cell/mm  decrease	600- 799	500 – 599	< 500
Monocytes – cell/mm  increase	1001-2000	2001-3000	>3000
Eosinophils - cell/mm  increase	871 - 950	951 - 1700	>1700
Basophils - cell/mm  increase	101 - 300	301 - 800	> 800
High Density Lipoproteins (HDL) Male – mg/dL	N/A	N/A	N/A
High Density Lipoproteins (HDL) Female – mg/dL	N/A	N/A	N/A
Total Carbon Dioxide – mEq/L	N/A	N/A	N/A
Total Cholesterol – mg/dL	N/A	N/A	N/A
Low Density Lipoprotein Cholesterol, Direct – mg/dL	N/A	N/A	N/A
Triglycerides – mg/dL	N/A	N/A	N/A
Laboratory Adverse Events* (Urine)			
Protein	1+	2+	>2+
Glucose	1+	2+	>2+
Blood (microscopic) - red blood cells per high power field (rbc/hpf)**	3-10**	11-50**	>50 and/or gross blood**

\*Abnormal laboratory values, performed as part of hematology, chemistry panel, or urinalysis but not listed in Appendix B, VT-1598 TOXICITY GRADING CRITERIA FOR NORMAL HUMAN SUBJECTS, will be evaluated by the study clinicians, recorded in the source document and, if clinically significant, considered AEs and graded according to the criterion described in [Section 8.1](#).

Adverse Events*	Mild (Grade 1)	Moderate (Grade 2)	Severe (Grade 3)
-----------------	-------------------	-----------------------	---------------------

\*\* Hematuria during active menses is considered not clinically significant.

Vital Sign Adverse Events	Mild (Grade 1)	Moderate (Grade 2)	Severe (Grade 3)
Fever (°C)	38.0 – 38.4	38.5 – 38.9	39.0 – 40
(°F)	100.4 – 101.1	101.2 – 102.0	102.1 – 104
ECG – QTcF (ms)	> 30 but ≤60 above baseline	>60 above baseline to ≤500	>500
Tachycardia – (beats per minute)	101 – 115	116 – 130	>130
Bradycardia – (beats per minute)	50-54 if baseline >60	45-49 if baseline >60	<45 if baseline >60
	45-50 if baseline ≤ 60	40-44 if baseline ≤ 60	<40 if baseline ≤ 60
Hypertension (systolic) – mmHg	141 – 150	151 – 155	>155
Hypertension (diastolic) – mmHg	91 – 95	96 – 100	>100
Hypotension (systolic) – mmHg	85 – 89	80 – 84	<80
Respiratory Rate – breaths per minute	17-20	21-25	>25
Nausea/vomiting	No to mild interference with activity or 1 to 2 episodes/24 hours	Moderate interference with activity or >2 episodes/24 hours	Prevents daily activity, requires outpatient IV hydration
Diarrhea	2 - 4 loose stools or	5-6 stools or 400 – 800	7 or more watery stools or >800gms/24 hours or

Vital Sign Adverse Events	Mild (Grade 1)	Moderate (Grade 2)	Severe (Grade 3)
	< 400 gm/24 hours	gm/24 hours	requires outpatient IV hydration
Headache	No interference with activity	Repeated use of non-narcotic pain reliever > 24 hours or some interference with activity	Significant; any use of narcotic pain reliever or prevents daily activity
Fatigue	No interference with activity	Some interference with activity	Significant; prevents daily activity
Adverse Events – Other			
Illness or clinical AE (as defined according to applicable regulations)	No interference with activity	Some interference with activity, not requiring medical intervention	Prevents daily activity and requires medical intervention

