#### Adverse Events Grading

AEs will be assessed by a licensed study physician listed on the Form FDA 1572 as the site principal investigator or appropriate sub-investigator using a protocol-defined grading system. For events not included in the protocol-defined grading system ([Section 8](#) Assessment of Safety/[Appendix B](#) VT-1598 Toxicity Grading Criteria for Normal Human Subjects), the following guidelines will be used to quantify severity:

- Mild (Grade 1): Events require minimal or no treatment and do not interfere with the subject's daily activities;

- 
- Moderate (Grade 2): Events result in a low level of inconvenience or concern with therapeutic measures. Moderate events may cause some interference with functioning and daily activities and use of over the counter medication;
  - Severe (Grade 3): Events interrupt the subject's usual daily activities and may require systemic drug therapy or other treatment. Severe events are usually incapacitating.

**Relationship to Study Products:** The assessment of the relationship of an AE to the administration of study product is made only by those with the training and authority to make a diagnosis and listed on the Form FDA 1572 as an investigator based on all available information at the time of the completion of the eCRF. Whether the AE is related or not, is not a factor in determining what is or is not reported in this trial. If there is any doubt as to whether a clinical observation is an AE, the event should be reported.

In a clinical trial, the study product must always be suspect. To help assess, the following guidelines are used.

- Related – There is a reasonable possibility that the study product caused the adverse event. Reasonable possibility means that there is evidence to suggest a causal relationship between the study product and the adverse event;
- Not Related – There is not a reasonable possibility that the administration of the study product caused the event.

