## **8.6 Halting Rules**

### **8.6.1 Study Halting Criteria**

If any of the criterion below are met, the study will be suspended (enrollment and dosing), and the SMC ad hoc meeting will convene:

- Any SAE, regardless of the relationship to the study drug, throughout duration of study, unless confirmed to be of reasonable alternative etiology.

- 
- 5 or more subjects in study (cumulative among all cohorts) experience a same grade 2 (or higher) related AE (laboratory or systemic) which is coded in the same high-level group term (HLGT) per MedDRA coding, throughout duration of study.

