## 8.6.2 Dose Escalation Halting Criteria

### Sentinel Subject Halting Rules

If any of the criterion below are met, the cohort will be suspended (enrollment and dosing), and the SMC ad hoc meeting will convene:

- Any SAE (regardless of the relationship to the study drug) through Day 3 of the study;
- any Grade 2 (or higher) adverse event (laboratory or systemic) if not resolved within 1 day, through Day 3 of the study.

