### Cohort Dose Escalation Halting Rules

If any of the criterion below are met, the escalation to the next cohort will be suspended (enrollment and dosing), and the SMC ad hoc meeting will convene.

- 2 or more subjects in a cohort experience the same grade 2 (or higher) related AE (laboratory or systemic) which is coded in the same HLGT per MedDRA coding, through Day 7 of the study;
- 2 or more subjects within a cohort with post-dose QTcF > 500 ms or change from baseline >60 ms through Day 7 of the study.

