### 10.5.2 Clinical Safety Labs, Vital Signs, and Electrocardiograms

Baseline for clinical safety labs, vital signs, and ECGs will be defined as the last result obtained before the dose of study product. Clinical safety labs, vital signs, and ECGs results and changes from baseline will be summarized by treatment arm and visit. Clinical safety labs and vital signs will be graded ([Appendix B](#)) and summarized by severity, treatment arm, and visit. If triplicate ECG measurements were performed at the same visit, then baseline is the mean value of the measurements for the visit closest to, but before, administration of study drug. Similarly, for analyses of change from baseline, mean values will be used in the case of replicate measurements at a single visit post-baseline.

Treatment-emergent abnormal laboratory test results will be identified. Treatment-emergent abnormal laboratory tests are tests for which the result was not graded as mild or worse at baseline but graded as mild or worse after dosing. Laboratory tests graded as mild at baseline,

but moderate or worse any time after dosing will also be regarded as treatment-emergent abnormal laboratory test results.

ECG measurements will include heart rate, RR interval, QT interval, QTcF interval, PR interval, and QRS duration. Baseline for ECG measurements is defined per protocol as the value pre-dosing on Day 1. Change from baseline will be summarized descriptively by regimen at each scheduled evaluation. QTc results will be summarized categorically according to the ICH Guideline E14 “Clinical Evaluation of QT/QTc Interval Prolongation and Proarrhythmic Potential for Non-Antiarrhythmic Drugs” (October 2005).

- QTcF >450 ms;
- QTcF >450 ms, males only;
- QTcF >470 ms, females only;
- QTcF >480 ms;
- QTcF >500 ms;
- QTcF increases from baseline by at least 30 ms but less than 60 ms;
- QTcF increases from baseline by at least 60 ms.

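### SAP Table 4 starts total bilirubin Grade 2 at 1.60 mg/dL where Appendix B implies just above 1.50, and neither fever scale has a grade above 40 °C

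*Protocol*

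**What the plan says.** Protocol Section 10.5.2 ties the analysis to Appendix B: "Clinical safety labs and vital signs will be graded" by that appendix and then summarised by severity, arm and visit. In Appendix B, total bilirubin is Grade 1 at "1.1 - ≤ 1.25 x ULN", Grade 2 at ">1.25 - ≤ 1.50 x ULN", and Grade 3 above 1.50 x ULN. The three bands adjoin.

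SAP Section 4.5 grades laboratory results by SAP Table 4 instead, which gives total bilirubin in mg/dL: 1.32-1.50 (Grade 1), 1.60-1.80 (Grade 2) and above 1.80 (Grade 3). SAP Table 28 counts subjects by these grades at each visit, with a Maximum Severity Post Baseline row and an Any Parameter block. Under the notes to SAP Table 23, a result that is out of range but in no grade is listed as ONR (out of normal range).

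For fever, Grade 3 is 39.0-40 °C (102.1-104 °F) in both Appendix B and SAP Table 5. Nothing is defined above that.

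**The concern.** Table 4 should be a unit conversion of Appendix B, and for total bilirubin it is not. The interval between 1.50 and 1.60 mg/dL belongs to no grade. The effect is not monotone: a result of 1.50 is counted as Mild, a result of 1.55 is in no severity column, and a result of 1.60 is Moderate. The subject with 1.55 stays in the Table 28 denominator, and so reads as having no graded elevation.

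The protocol names hepatotoxicity as a risk of the azole class and says that it will monitor for the class effects. With six active subjects per cohort, one missed result is 1/6, or 17%, of a dose group. The label in Table 23 does not repair this, because the same label is used there for graded results that are not worse than baseline.

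The mismatch is not declared as a choice. Protocol Section 10 says that departures from the protocol analyses will be described in the SAP, and SAP Section 15 describes only the change to the Tmax comparison.

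**Working it through.** **Inputs.** Appendix B multipliers for total bilirubin: 1.1, 1.25 and 1.50 x ULN. SAP Table 4 limits: 1.32, 1.50, 1.60 and 1.80 mg/dL. The ULN is not printed, so it has to be derived.

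**Step 1: implied ULN = printed limit / Appendix B multiplier.**
- Grade 1 lower limit: 1.32 / 1.1 = 1.20
- Grade 1 upper limit: 1.50 / 1.25 = 1.20
- Grade 2 upper limit: 1.80 / 1.50 = 1.20

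These three limits agree exactly on 1.2 mg/dL. The Grade 2 lower limit should be anything above 1.25 x 1.2 = 1.50. The printed 1.60 is 1.60 / 1.2 = 1.33 x ULN, which is not a cut-point in Appendix B.

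**Step 2: Appendix B in mg/dL at ULN 1.2, beside Table 4.**

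| Grade | Appendix B | SAP Table 4 |
|---|---|---|
| 1 | 1.32 to 1.50 | 1.32-1.50 |
| 2 | above 1.50 to 1.80 | 1.60-1.80 |
| 3 | above 1.80 | > 1.80 |

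**Step 3: compare the two scales value by value from 1.00 to 2.00 mg/dL.**
- In steps of 0.01, nine values differ: 1.51 to 1.59. Their multiples run from 1.51 / 1.2 = 1.258 to 1.59 / 1.2 = 1.325, all inside the Appendix B Grade 2 band. That band holds thirty such values (1.51 to 1.80), so 9/30 = 30% of it is ungraded.
- In steps of 0.1, no value differs.

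**Step 4: neighbouring rows of Table 4.** The Grade 1 and Grade 2 limits adjoin for male AST (100/100.1), male ALT (102.5/102.51), direct bilirubin (0.25/0.26) and indirect bilirubin (1.49/1.491). Total bilirubin departs from that pattern. Male alkaline phosphatase shows a similar break: Grade 1 ends at 260 and Grade 2 starts at 264, although 260/2 = 390/3 = 130 gives an Appendix B Grade 2 that begins just above 260. This suggests transcription slips rather than intent.

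**Step 5: fever.** 40 x 9/5 + 32 = 104, so the Celsius and Fahrenheit bands close at the same point. The Grade 3 bands for heart rate, blood pressure and respiratory rate are open-ended.

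**The case against.** The strongest objection is that the gap may be empty. The documents do not say to how many decimals the laboratory reports total bilirubin. A Grade 2 start of 1.60 after a Grade 1 end of 1.50 is what reporting to 0.1 mg/dL would produce. Limits such as 1.32 do not prove finer reporting, since entries like 102.51 for ALT or 1.491 for indirect bilirubin look like products of multiplication. This stands, and it makes the practical effect conditional. It does not make the cell agree with Appendix B.

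A second objection is that a value of 1.55 is not lost. It is listed in Table 23, counted as abnormal high in Table 27, and enters the change-from-baseline summary in Table 29. If reported as an adverse event, it appears in the AE tables at the physician's grade. This also stands, and it confines the effect to the severity displays.

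A reader might go further and infer that halting-level values escape the safety rules. The rules do count Grade 2 laboratory events: "5 or more subjects in study (cumulative among all cohorts) experience a same grade 2 (or higher) related AE (laboratory or systemic") at study level, "2 or more subjects in a cohort experience the same grade 2 (or higher) related AE (laboratory or systemic") at cohort level, and "any Grade 2 (or higher) adverse event (laboratory or systemic) if not resolved within 1 day" for sentinels. But "AEs will be assessed by a licensed study physician listed on the Form FDA 1572", on the protocol scale, and that scale has no bilirubin gap. The SAP points back to Protocol Section 8.6 for halting and sets no scale of its own for it. Protocol Section 3.1.5 has the data centre's halting report run on data entered in EDC, and no text says that the report uses SAP Table 4.

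A reader might also take the direct bilirubin row as proof that the table fails at either precision, because no one-decimal result can fall in its Grade 1 band of 0.22-0.25. That assumes a reporting precision, shared by both tests, which the documents do not give. The row itself reproduces Appendix B exactly (0.22/1.1 = 0.25/1.25 = 0.30/1.5 = 0.20), so it is no discrepancy.

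**Conclusion.** SAP Table 4 does not reproduce Appendix B for total bilirubin. The lower limit of Grade 2 is wrong by the table's own implied ULN of 1.2 mg/dL. The effect depends on reporting precision. At 0.01 mg/dL, nine of the thirty Grade 2 values have no severity in Table 28, and its Maximum Severity and Any Parameter rows miss them unless another graded result from the same subject fills the row. At 0.1 mg/dL nothing changes. Dose-escalation and halting decisions are not shown to be affected.

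The fever point is smaller still. A reading above 40 °C has no severity column in Table 39, and is unlikely in healthy volunteers. One might infer that such a fever would go ungraded as an adverse event, but the documents do not say so: all adverse events are captured and graded by a physician, and Appendix B has a general row for clinical illness. The fallback guideline is worded "For events not included in the protocol-defined grading system", and fever is in that system, so the route is not cleanly specified. Both items are minor corrections to tables.

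**What to change.** In SAP Table 4, change total bilirubin Grade 2 from 1.60-1.80 to >1.50-1.80, so that it matches Appendix B at any reporting precision. Check the male alkaline phosphatase row against Appendix B at the same time. Reconcile the fever rows of Appendix B and SAP Table 5 so that every reading above the Grade 2 band has a grade.

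The cost is a few cell edits and a rerun of the affected severity tables, with no new data. The only consequence is that some results now outside the scale may be counted as Grade 2, as the protocol already requires.

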$AUC_{0\text{-}last}$	AUC to the last measurable concentration
$AUC_{0\text{-}inf}$	AUC extrapolated to infinity
$\%AUC_{ex}$	Percentage of $AUC_{0\text{-}inf}$ obtained by extrapolation
BMI	Body Mass Index
BQL	Below the Limit of Quantification
CHEM	Chemistry
CI	Confidence Interval
CL/F	Apparent Oral Clearance
CL_R	Renal Clearance of Drug or Metabolite
C_{max}	Maximum Concentration
COAG	Coagulation
CRF	Case Report Form
CRU	Clinical Research Unit
CS	Clinically Significant
CSR	Clinical Study Report
CV	Coefficient of Variation
DMID	Division of Microbiology and Infectious Diseases
DSMB	Data and Safety Monitoring Board
ECG	Electrocardiogram
eCRF	Electronic Case Report Form
EDC	Electronic Data Capture
FDA	Food and Drug Administration

List of Abbreviations (continued)

FIH	First-In-Human
FSH	Follicle Stimulating Hormone
GGT	Gamma-Glutamyl Transferase
GM	Geometric Mean
hCG	Human Chorionic Gonadotropin
HBsAg	Hepatitis B Surface Antigen
HCV	Hepatitis C Virus
HDL	High Density Lipoproteins
HEM	Hematology
HIV	Human Immunodeficiency Virus
HLGT	High-Level Group Term
ICH	The International Council for Harmonization
ICON BAL	ICON Bioanalytical Laboratory
ID	Identification
ISM	Independent Safety Monitor
IUD	Intrauterine Devices
LC-MS/MS	Liquid Chromatography with Tandem Mass Spectrometry
LDL	Low Density Lipoprotein
LLOQ	Lower Limit of Quantification
MedDRA®	Medical Dictionary for Regulatory Activities
Max	Maximum
Min	Minimum
MOP	Manual of Procedures
N	Number (typically refers to subjects)
NCA	Noncompartmental Analysis
NCS	Not Clinically Significant
NIAID	National Institute of Allergy and Infectious Diseases
NIH	National Institutes of Health
ONR	Out of Normal Range
PI	Principal Investigator

List of Abbreviations (continued)

PK	Pharmacokinetics
PT	Preferred Term
PTT	Partial Thromboplastin Time
QNS	Quantity not Sufficient
RBC	Red Blood Cells
SAD	Single Ascending Dose
SAE	Serious Adverse Event
SAP	Statistical Analysis Plan
SD	Standard Deviation
SDCC	Statistical and Data Coordinating Center
SMC	Safety Monitoring Committee
SOC	System Organ Class
$t_{1/2}$	Apparent terminal elimination half-life
T_{last}	Time of the last measurable concentration
T_{max}	Time to obtain maximum concentration
UA	Urinalysis
V_d/F	Apparent volume of distribution during terminal phase
VS	Vital Sign
WBC	White Blood Cell
λ_z	Apparent first-order terminal elimination rate constant

1. PREFACE

The Statistical Analysis Plan (SAP) for “A Phase 1, First-In-Human, Randomized, Double-Blind, Placebo Controlled, Single Dose-Escalation Study to Evaluate the Safety and Pharmacokinetics of Single Oral Doses of VT-1598 in Healthy Adult Subjects” (Division of Microbiology and Infectious Diseases (DMID) Protocol 17-0087) describes and expands upon the statistical information presented in the protocol.

This document describes all planned analyses and provides reasons and justifications for these analyses. It also includes sample tables, listings, and figures planned for the final analyses. This SAP follows the International Conference on Harmonisation of Technical Requirements for Registration of Pharmaceuticals for Human Use (ICH) Guidelines, as indicated in Topic E3 (Structure and Content of Clinical Study Reports (CSRs)) [1], and more generally is consistent with Topic E8 (General Considerations for Clinical Trials) [2], and Topic E9 (Statistical Principles for Clinical Trials) [3]. The structure and content of the SAP provides sufficient detail to meet the requirements identified by the Food and Drug Administration (FDA) and ICH, while all work planned and reported for this SAP will follow internationally accepted guidelines published by the American Statistical Association and the Royal Statistical Society of statistical practice.

This document contains four sections: (1) a review of the study design, (2) general statistical considerations, (3) comprehensive statistical analysis methods for the safety and pharmacokinetic (PK) outcomes, and (4) a list of proposed tables, figures, and listings. Within the table, figure, and listing mock-ups (Appendices 1, 2, and 3), references to CSR sections are included. Any deviation from this SAP will be described and justified in the CSR. The reader of this SAP is encouraged to also review the study protocol for details on conduct of the study and the operational aspects of clinical assessments.

